10.2 Interim analysis

Not applicable.

11. ETHICAL CONSIDERATIONS

11.1 Regulation statement

This study will be conducted according to the principles of the Declaration of Helsinki (59th version, Seoul, October 2008) and in accordance with the Medical Research involving Human Subjects Act (WMO) and other guidelines, regulations and Acts.

11.2 Recruitment and consent

At the Radboudumc and LUMC, respectively 90 and 45 laparoscopic donor nephrectomies are performed annually. All eligible donors will be screened. With an inclusion rate of approximately 80%, we expect that the screening (and inclusion period) will be 11 months.

Informed consent is obtained at least two weeks after providing written information about the study. During this two-week interval, an independent physician can be consulted for questions. At the day of hospital admission, one day before surgery, informed consent will be obtained. Then, one, unique number will be assigned (study number).

11.3 Objection by minors or incapacitated subjects

Not applicable.

11.4 Benefits and risks assessment, group relatedness

The burden for participants in this study is mainly related to the evaluation of the endpoints during the early postoperative phase. Assessment of the differential pain scores and the QOR-40 questionnaire will take approximately 10 minutes per time-point (-18h, 1h, 4h, 8h, 24h and 48h after detubation). As the use of a deep NMB with a standard insufflations pressure improves the quality of the surgical field, there are no risks related to the surgery. A deep neuromuscular block can be achieved by higher doses of rocuronium as compared to the routine intubation dose.

The participants of this study are approved for live kidney donation. One of the selection criteria is a glomerular infiltration rate above 59-85 ml/min/1.73m² (depending on age) to provide sufficient residual (donor) renal function post donation. According to Li *et al* the early decrease of the glomerular filtration rate after kidney donation is approximately 15-20 ml/min/1.73m² (10). Therefore a higher dose of rocuronium in living kidney donors is safe, as the plasma clearance of rocuronium in patients with moderate to severe renal

dysfunction is only slightly reduced (1ml/kg/min) as compared to patients with normal renal function (rocuronium clearance 3.7 ml/kg/min).

To overcome the extended effects of deep neuromuscular blockade that may lead to airway obstruction, hypoxia, pneumonia and/or atelectasis, sugammadex is administered to antagonize the effects of rocuronium. Sugammadex is a rapid antagonist of neuromuscular blockade by rocuronium that is given immediately after surgery. Randomized controlled trials have shown that sugammadex can be safely administered in patients, without dose adjustments for young, elderly or obese patients and that it can also be safely administered in patients with mild or moderate renal impairment (creatinine clearance ≥ 30 and < 80 mL/min) (12).

Elimination of the rocuronium-sugammadex will take longer in donors, because of the slightly decreased glomerular filtration rate, but since the rocuronium is inactivated by sugammadex, there is no risk at recurrence of neuromuscular blockade.

A recent study performed by Martini *et al.* has shown that deep neuromuscular blockade improves surgical conditions with reduced postoperative pain scores after laparoscopic surgery (1). Moreover, preliminary data of our recently performed Leopard-3 study, show that the mean SRS (surgical rating scale) was significantly better during deep NMB with less opiate consumption (2). Altogether, we expect that the use of deep NMB during LDN reduces postoperative pain scores and/or analgesia consumption. This may improve the early quality of recovery of live kidney donors.

11.5 Compensation for injury

The Radboudumc has an insurance in accordance with the legal requirements in the Netherlands (Article WMO and the Measure regarding Compulsory Insurance for Clinical Research in Humans of 23th June 2003). This insurance provides cover for damage to research subjects though injury or death caused by the study.

1. € 650.000,-- (i.e. sixhundred and fifty thousand Euro) for death or injury for each subject who participates in the Research
2. € 5.000.000,-- (i.e. five million Euro) for death or injury for all subjects who participate in the Research
3. € 7.500.000,-- (i.e. seven million fivehundredthousand Euro) for the total damage incurred by the organisation for all damage disclosed by scientific research for the Sponsor as 'verrichter' in the meaning of said Act in each year of insurance coverage

The insurance applies to the damage that becomes apparent during the study or within 4 years after the end of the study.

11.6 Incentives

Not applicable.

12. ADMINISTRATIVE ASPECTS, MONITORING AND PUBLICATION

12.1 Handling and storage of data and documents

Subjects will be coded by a numeric code in order to create an anonymous dataset. A Castor database will be developed and used for data management. Investigators have access to this code and will store the subject identification code list at a separate location from the dataset.

Data will be securely stored in the database of the department of surgery of the Radboud university medical center accessible to the investigators, in accordance with the Dutch Personal Data Protection Act.

12.2 Monitoring and Quality Assurance

In our opinion, this study adds a small chance (“kleine kans”) of mild damage (“lichte schade”) and consequently adds a negligible risk (“verwaarloosbaar risico”) according to the risk classification of the “Nederlandse Federatie van Universitair Medische Centra” (NFU). Monitoring will be conducted in accordance with negligible risk monitoring guidelines of the NFU, which will be reported in a monitorplan.

Risk classification in relation to the chance and severity of damage (Dutch versions)

	Lichte schade	Matige schade	Ernstige schade
Kleine kans	Verwaarloosbaar risico	Verwaarloosbaar risico	Matig risico
Matige kans	Verwaarloosbaar risico	Matig risico	Hoog risico
Grote kans	Matig risico	Hoog risico	Hoog risico

12.3 Amendments

Not applicable.

12.4 Annual progress report

The investigator will submit a summary of the progress of the trial to the accredited METC once a year. Information will be provided on the date of inclusion of the first subject, numbers of subjects included and numbers of subjects that have completed the trial, serious adverse events/serious adverse reactions, other problems and amendments.

12.5 Temporary halt and (prematurely) end of study report

The investigator will notify the accredited METC of the end of the study within a period of 8 weeks. The end of the study is defined as the last patient’s last visit.

The investigator will notify the METC immediately of a temporary halt of the study, including the reason of such an action.

In case the study is ended prematurely, the investigator will notify the accredited METC within 15 days, including the reasons for the premature termination.

Within one year after the end of the study, the investigator/ will submit a final study report with the results of the study, including any publications/abstracts of the study, to the accredited METC.

12.6 Public disclosure and publication policy

The study will be registered at ClinicalTrials.gov. Results will be published in a peer-reviewed international journal.

13. STRUCTURED RISK ANALYSIS

Not applicable.

2	Poor conditions	There is a visible laparoscopic field, but the surgeon is severely hampered by inadequate muscle relaxation with continuous muscle contractions, movements or both with the hazard of tissue damage.
3	Acceptable conditions	There is a wide visible laparoscopic field but muscle contractions, movements or both occur regularly causing some interference with the surgeon's work.
4	Good conditions	There is a wide laparoscopic field with sporadic muscle contractions, movements or both.
5	Optimal conditions	There is a wide visible laparoscopic working field without any movement or contractions.

Table 3.

Overview of variables and time-points.

	-18h	1h	4h	8h	24h	48h
QOR-40	x				x	x
Components of pain	x	x	x	x	x	x
Analgesia use	x	x	x	x	x	x
Discharge criteria				x	x	x
Evaluation of complications					x	x

[figure not shown]
Table 4.

Overview of variables and procedures/techniques.

Study parameters/endpoints	Procedure, technique and/or tests
Quality of recovery	Quality of recovery 40 questionnaire (appendix 1)
Surgical rating score	Peri-operative evaluation (table 2)
Pain	Components of pain
Medication use	Daily evaluation of electronic patient dossier
Nausea/vomiting	Daily evaluation during hospital admission
Surgical parameters	Intra-operative evaluation by the surgeon
Evaluation of post-operative complications	Daily evaluation during hospital admission

Figure 1.

Study Flow Chart

Appendix 1.

QOR-40 questionnaire.

Vragenlijst over kwaliteit van herstel

Om een inzicht te krijgen in het herstel na de operatie die u heeft ondergaan, vragen wij u deze vragenlijst in te vullen.

Geef u daarvoor alstublieft bij elke vraag het antwoord dat het beste weergeeft hoe u zich de laatste 24 uur voelde. Dit gebeurt op een schaal van 1-5. Boven de gevallen staat de betekenis van de getallen.

Welbevinden	Helemaal niet waar			Helemaal waar	
Ik kan gemakkelijk ademen	1	2	3	4	5
Ik heb goed geslapen	1	2	3	4	5
Het eten heeft me gesmaakt	1	2	3	4	5
Ik voel me uitgerust	1	2	3	4	5

Gevoelens	Helemaal niet waar			Helemaal waar	
Ik voel me over het algemeen goed	1	2	3	4	5
Ik heb de situatie/mezelf in de hand	1	2	3	4	5
Ik voel me op mijn gemak	1	2	3	4	5

Zelfredzaamheid	Helemaal niet waar			Helemaal waar	
Ik kan goed een gesprek voeren	1	2	3	4	5
Ik kan mezelf wassen en tanden poetsen	1	2	3	4	5
Ik kan mezelf verzorgen	1	2	3	4	5
Ik kan schrijven	1	2	3	4	5
Ik kan werken/ werkzaamheden thuis verrichten	1	2	3	4	5

Steun	Helemaal niet waar			Helemaal waar	
Het is mogelijk in het ziekenhuis met artsen en verpleegkundigen te spreken	1	2	3	4	5
Het is mogelijk met familie en vrienden te spreken	1	2	3	4	5
Ik wordt gesteund door de artsen in het ziekenhuis	1	2	3	4	5
Ik word gesteund door de verpleegkundigen in het ziekenhuis	1	2	3	4	5
Ik wordt gesteund door familie en vrienden	1	2	3	4	5
Ik begrijp uitleg en adviezen	1	2	3	4	5

PAS OP: HELEMAAL WAAR EN WAAR ZIJN NU OMGEDRAAID!

Welbevinden	Helemaal waar			Helemaal niet waar	
Ik heb last van misselijkheid	1	2	3	4	5
Ik heb overgegeven	1	2	3	4	5
Ik moet kokhalzen	1	2	3	4	5
Ik voel me rusteloos	1	2	3	4	5
Ik heb last van trillen of beven	1	2	3	4	5
Ik heb last van rillerigheid	1	2	3	4	5
Ik heb het te koud	1	2	3	4	5
Ik heb last van duizeligheid	1	2	3	4	5

Gevoelens	Helemaal waar			Helemaal niet waar	
Ik heb naar gedroomd	1	2	3	4	5
Ik voel me angstig	1	2	3	4	5
Ik ben boos	1	2	3	4	5
Ik voel me somber	1	2	3	4	5
Ik voel me alleen	1	2	3	4	5
Ik heb moeite om in slaap te komen	1	2	3	4	5

Steun	Helemaal waar			Helemaal niet waar	
Ik voel me verward	1	2	3	4	5

Pijn en klachten	Helemaal waar			Helemaal niet waar	
Ik heb matige pijn	1	2	3	4	5
Ik heb ernstige pijn	1	2	3	4	5
Ik heb hoofdpijn	1	2	3	4	5
Ik heb spierpijn	1	2	3	4	5
Ik heb rugpijn	1	2	3	4	5
Ik heb een pijnlijke mond	1	2	3	4	5
Ik heb een pijnlijke keel	1	2	3	4	5

Appendix 2.

Vragenlijst over werk en zorg.

Vragenlijst over werk en zorg

In deze vragenlijst wordt u gevraagd in hoeverre u weer in staat bent om te werken en hoeveel extra zorg u de afgelopen week nodig hebt gehad.

1. Heeft u de afgelopen week de huisarts vanwege de operatie bezocht?

0 nee

0 ja, Hoe vaak? _____
—

Waarom? _____

2. Heeft u de afgelopen week een dokter in het ziekenhuis bezocht vanwege de operatie?

0 nee

0 ja, Hoe vaak? _____
—

Waarom? _____

3. Bent u de afgelopen week nogmaals opgenomen in het ziekenhuis vanwege de donor operatie?

0 nee

0 ja, Hoeveel dagen? _____
—

Waarom? _____

4. Heeft u de afgelopen week hulp nodig gehad van familie, vrienden of kennissen?

0 nee

0 ja, Hoeveel uur? _____

5. Heeft u de afgelopen week thuiszorg gehad?

0 nee

0 ja, Hoeveel uur? _____

6. Heeft u de afgelopen week betaalde hulp in de huishouding gehad?

0 nee

0 ja, Hoeveel uur? _____

7. Heeft u de afgelopen week gewerkt?

0 nee, in verband met de operatie *ga verder naar vraag 8*

0 nee, reeds voor de operatie niet (meer) werkzaam *ga verder naar vraag 8*

0 nee, omdat _____ *ga verder naar vraag 8*

0 ja, Op welke datum bent u weer gaan werken? _____

Hoeveel uur heeft u de afgelopen week gewerkt? _____

8. Hoeveel procent van uw dagelijkse bezigheden, die u voor de operatie ook deed, heeft u kunnen uitvoeren deze week? (zoals huishoudelijke werkzaamheden, hobby's en persoonlijke verzorging)

_____ (tussen 0 en 100%)

Dank u wel voor het invullen!

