8.1.3 Other study parameters

Baseline parameters: age, gender, length, weight, body mass index, comorbidity, side of nephrectomy.

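### In the 4-week work-and-care form, the help hours (questions 4-6) and work hours (question 7) lack a pre-operative reference, so they cannot be read as extra care or degree of return to work

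*Combined protocol and SAP*

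**What the plan says.** Section 8.1.2 lists the work-and-care questionnaire among the secondary endpoints, under follow-up after 4 weeks. The form is in Appendix 2. Its preface states its purpose: "in hoeverre u weer in staat bent om te werken en hoeveel extra zorg u de afgelopen week nodig hebt gehad", that is, how far the donor can work again and how much extra care was needed in the past week.

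The first three care questions are tied to the operation:

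- GP visits: "Heeft u de afgelopen week de huisarts vanwege de operatie bezocht"
- hospital doctor visits: "Heeft u de afgelopen week een dokter in het ziekenhuis bezocht vanwege de operatie"
- readmission: "Bent u de afgelopen week nogmaals opgenomen in het ziekenhuis vanwege de donor operatie"

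The next three ask for hours of help from family and friends (question 4), home care (question 5) and paid household help (question 6: "Heeft u de afgelopen week betaalde hulp in de huishouding gehad"). None of them mentions extra help or the operation.

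Question 7 covers work. It separates donors not working because of the operation, those already not working before it, and those not working for another reason. Donors who are working give the date of return and then answer "Hoeveel uur heeft u de afgelopen week gewerkt".

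The baseline list in section 8.1.3 reads "Baseline parameters: age, gender, length, weight, body mass index, comorbidity, side of nephrectomy". It contains no working hours and no existing help.

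**The concern.** The preface promises two relative quantities: care beyond what the donor normally has, and the extent of return to work. Both need a reference to the situation before surgery. Questions 4-6 and the hours in question 7 have none.

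A donor with a long-standing cleaner can truthfully answer yes to question 6 and give hours unrelated to donation. Because questions 1-3 name the operation explicitly, a respondent may reasonably take questions 4-6 as not limited to it. For work, a part-time donor who is fully back can record fewer hours than a full-time donor who is half back.

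At stake is the interpretation of a listed secondary endpoint. If the reference is not collected, it cannot be restored at analysis.

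**Working it through.** **1. The plan's own figure.** Section 4.4 gives a difference of 10 points, SD 15, alpha 5% and power 90%. Sidedness is not stated; two-sided reproduces the result: n = 2 × (1.96 + 1.2816)² × 15² / 10² = 2 × 10.508 × 2.25 = 47.3, rounded up to 48 per group. This sizes the trial for QOR-40 at 24 hours. No figure is given for the work-and-care form, so nothing stated in the plan changes.

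**2. The form, question by question.**

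| Question | Content | Limited to extra or operation-related? | Pre-operative reference |
|---|---|---|---|
| 1 | GP visit | Yes | Not needed |
| 2 | Hospital doctor visit | Yes | Not needed |
| 3 | Readmission | Yes | Not needed |
| 4 | Help from family or friends, hours | No, but asks about help needed | None |
| 5 | Home care received, hours | No | None |
| 6 | Paid household help received, hours | No | None |
| 7 | Work status, reason, date of return, past-week hours | The reason is separated out | None for hours |
| 8 | Percentage of pre-operative daily activities | n/a | Built in, but the examples are household tasks, hobbies and personal care, not paid work |

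Three of the six care questions carry the limit and three do not.

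**3. Is the reference collected elsewhere?** Section 8.1.3 has neither existing help nor working hours. At -18 h, Table 3 shows only QOR-40, components of pain and analgesia use. Section 8.1.2 places the form only at 4 weeks. No listed variable fills either gap.

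**4. Effect on help hours.** Write recorded hours as H = E + B, where E is extra help and B is whatever existing help the donor includes. B is zero for a donor who follows the preface.

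- Level: mean(H) = mean(E) + mean(B), so absolute hours overstate extra care to the extent that B is included.
- Difference between arms: under 1:1 randomisation (sections 5.1 and 8.2), mean(B) is equal in expectation in both arms and cancels, provided both arms read the question alike. The difference in H is then unbiased for the difference in E.
- Noise: if E and B are independent, Var(H)/Var(E) = 1 + r², with r = SD(B)/SD(E). For assumed r of 0.25, 0.5, 1 and 1.5 the ratio is 1.06, 1.25, 2.00 and 3.25. The documents say nothing about r, so these values show the direction and the dependence only.

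**5. Effect on work hours.** Degree of return = past-week hours / usual hours. For 20 hours worked, with assumed usual hours:

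| Usual hours | Degree of return |
|---|---|
| 20 | 20/20 = 100% |
| 24 | 20/24 = 83% |
| 32 | 20/32 = 62.5% |
| 40 | 20/40 = 50% |

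The ordering can also reverse: a 16-hour donor fully back records 16 hours, and a 40-hour donor half back records 20. The denominator is not collected, so these cases cannot be told apart by hours.

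**The case against.** The strongest reply is that much of the form works as intended. Questions 1-3 measure operation-related care. Question 7 gives return to work as status, reason and date without needing usual hours. Question 8 is anchored to activities before surgery. A reader might infer that the 4-week work and care data as a whole miss their stated purpose; the documents do not support that, and the gap is confined to the hours in questions 4-7.

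Nor is over-counting certain. Respondents read the preface about extra care first, and question 4 asks about help that was needed. Both will steer some donors, so the ambiguity lies mainly in questions 5 and 6.

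It can also be said that no planned analysis is shown to fail. The plan defines no variable derived from these hours, the form is absent from the endpoint table in section 10.1 and from Tables 3 and 4, and the secondary objective concerns pain and analgesia. This stands, and it keeps the point small. It does not remove it: section 8.1.2 lists the form as a secondary endpoint, and any reported hours would meet the same difficulty.

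**Conclusion.** The point holds for the hours in questions 4-6 and question 7. Hours of help may include help that predates donation, and among donors back at work the degree of return cannot be derived from hours. No other planned data repair this.

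The consequence is limited. The primary endpoint and the sample size are untouched. The arms remain comparable, resting on randomisation and on both arms reading the questions alike. What is lost is some precision and the ability to report absolute hours as extra care or as extent of return.

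A reader might go further and quote a loss of power or an inflation factor. That would need the prevalence of existing help, the spread of usual hours and the spread of the fraction of work resumed, none of which the documents give. The variance ratios above are conditional on assumed inputs and are not estimates for this trial. A reader might also make something of question 8 referring to this week rather than the past week; on a form about the past week that is a trivial wording difference with no demonstrated effect. This is a cheap improvement to one secondary questionnaire.

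**What to change.** 1. In questions 4, 5 and 6, add *extra, vanwege de operatie*, matching the preface and questions 1-3.
2. Ask usual pre-operative weekly working hours once, either within question 7 or at the existing -18 h questionnaire. The latter avoids recall and the routing in question 7, which sends donors not at work straight to question 8.
3. Report question 7 hours as a fraction of usual hours among donors who worked before surgery, counting those not yet back because of the operation as 0. That group is defined before treatment, so the randomised comparison is kept; restricting to donors already back would not keep it. Report return status and date alongside, and state in advance how donors off work for another reason are handled.

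The cost is a few words and one question, with no extra visit or patients. The downside is slightly less comparability with any earlier use of the form.
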